9.4 POWER FOR COGNITIVE COMPARISONS

9.4.1 ORIGINAL POWER ANALYSIS

We focus on the week 24 assessment of cognitive function in this power calculation given that the study is a randomized study, even though we are interested in comparing groups with respect to change in cognitive function between baseline and week 24. Studies recently conducted at Duke suggest that the standard deviation associated with a one-time assessment of executive function, a component of cognitive function, is approximately 30 units.

We anticipate that 120 of the 160 patients will have pre- and post-measurements of cognitive function. A two-tailed t-test conducted at the 0.05 level of significance (two-tailed) will have 80% power to detect a difference of 15.5.

9.4.2 REVISED POWER ANALYSIS

Collection of measures of health-related quality of life and cognition is plagued with mistiming and drop-outs due to factors described in Section 9.1.

For the purpose of the analyses that focus on the change in cognition between baseline and week 24, the follow-up assessment should have occurred within +/- 4 week window of the scheduled week 24 assessment.

With this adjustment, there are 94 patients (52 in Arm A and 42 in Arm B) that has pre- and post-measurements of cognitive function. Assuming a standard deviation of 30 units, a two-tailed t-test conducted at the 0.05 level of significance (two-tailed) will have 80% power to detect a difference of 17.6.

9.5 ADDITIONAL ANALYSES

The analyses described in Section 9.3 will also be conducted within subgroups defined by WHO grade (original or revised), and tumor markers which have been captured in the study database. Additionally, the joint effect of these clinical predictors, treatment assignment, and their interaction will be explored in the context of these models.

10 SECONDARY OBJECTIVE: THROMBOCYTOPENIA

The second secondary objective is to assess protection of bone marrow against chemotherapy-induced thrombocytopenia of standard RT and TMZ in combination with BMX-001 compared to standard RT and TMZ alone in newly diagnosed HGG patients.

10.1 ENDPOINT

The proportion of patients who experience grade 3 or 4 thrombocytopenia during concurrent temozolomide and radiation will be estimated within each treatment group. The proportion of patients who experience a platelet count less than 100K during concurrent temozolomide and radiation will also be estimated within each treatment group. The period of observation for these events will extend until 2 weeks after completion of radiation treatment.

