### 9.1.7 TMZ Treatment Plan

TMZ is an oral alkylating agent which has demonstrated anti-tumor activity as a single agent in the treatment of recurrent glioma. As stated previously, Stupp et al.[65] have demonstrated an increase in efficacy of TMZ in combination with RT in the adjuvant treatment of primary malignant gliomas. In addition, the regimen was considered safe. Non-hematological grade 2 toxicities included: Fatigue (26%), other constitutional symptoms (7%), rash and dermatologic side effects (9%), infection (1%), vision (14%), and nausea and vomiting (13%). Grade 3 / 4 non-hematological toxicities occurred <10%: Fatigue (7%), other constitutional symptoms (2%), rash and dermatologic side effects (1%), infection (3%), vision (1%), and nausea and vomiting with a  $5HT_3$ -RA (<1%). Thus, this safe and standard regimen will be utilized in this protocol. During the chemoradiation phase, daily TMZ therapy will be calculated at a dose of 75 mg per square meter of body surface area per day and be administered 7 days a week from the first until the last day of RT therapy or a total of 42 days. Weekly CBC with differential and CMP will begin at week 2 and continue through week 8. Platelet count is part of CBC with differential count. Additional clinical and laboratory assessments will be at the discretion of the RT therapist. During the adjuvant phase, 5-day TMZ therapy will be calculated at a dose of 150 or 200 mg/m^2 and be administered the first 5 days of a 28 day cycle. One cycle will consist of 28 days. If a subject cannot tolerate the 5-day TMZ and is switched to metronomic TMZ (low-dose, continuous TMZ), they will remain on the study and will complete all planned study endpoints. Use of Optune device will be allowed during the adjuvant phase with TMZ per NCCN guidelines and subjects will complete all planned study endpoints. If a subject completes only 6 cycles of temozolomide (vs. 12 cycles), they will remain in the study and subjects will complete all planned study endpoints through the planned 12 cycle timeframe. After that they will be continued to be followed for vital status.

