b Will transition to 5-day TMZ dosed at 150-200 mg/m^2 po daily for the 1st 5 days in 28-day cycle (Adjuvant Phase). Study assessments for HRQoL Measurements, and Hair Loss Evaluation will be obtained approximately every 8 weeks (+/- 2 weeks) when a subject returns for a Standard of Care visit, until tumor progression, death, or patient comes off of study. Cognitive testing will also be completed every 8 weeks and at SOC visits; Cognitive testing will continue after tumor progression. CBC with differential will be obtained approximately on Days 21 or 28 of each 28-day cycle, and CMP will be obtained approximately on Day 21 of each 28-day cycle, or per the ordering physicians Standard of care practice, during the adjuvant phase, until the subject comes off the study. If subject is transitioned to metronomic temozolomide because of poor tolerance to 5-day temozolomide, then they will continue to be on study. Moreover, if Optune is used during the adjuvant phase, then they will continue to be on study. Adjuvant temozolomide can start up to 4 weeks after radiation therapy has completed.

c Starting at Loading dose day or Day -5 to 0, this will occur once every other week during weeks 1-8. This may be modified to meet standard of care scheduling for patient visits.

d Weekly CBCs and CMPs will begin at week 2 and continue through week 8. Platelet count is part of CBC with differential count.

e ECG will be done at screening for all subjects. For subjects in Arm A, ECG will also be obtained before the loading dose is administered (within 5 to 60 minutes before the dose), and at 60 (+/- 15 min) minutes after the loading dose. Pre-dose (within 5 to 60 minutes before the dose), and Post-dose ( 60 +/- 15 min) ECGs will also be collected at the Week 1 first maintenance dose and on either one of the BMX-001 injection days in Week 4.

f See Appendix B for timing of PK sampling, Day 8 and Day 36 only. Phase 1- all subjects, Phase 2- 6 subjects at Duke. g HRQoL measurements will be completed during Screening as a baseline and then approximately every 8 weeks when a subject returns for a Standard of Care visit during the Adjuvant Phase. These assessments should be completed prior to other study-related evaluations at study visits, if at all possible.

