h DTI/Susceptibility Imaging is for clinical centers selected by the sponsor and completed at baseline, during the Adjuvant Phase before the start of the first cycle of adjuvant temozolomide, as well as 6 months (approximately 24 weeks, +/- 2 weeks) after radiotherapy/chemotherapy

i Toxicity assessment will continue to be obtained at every SOC clinic visit during the Adjuvant Phase for a minimum of 30 days after last BMX-001 treatment for subjects receiving BMX-001 or last chemo/RT for subjects not receiving BMX-001, and also followed for any unresolved adverse events considered related to study therapy.

j For BMX-001, this dose will be the loading dose. In Phase 2- Applicable only for patients in Arm A.

k For BMX-001, doses (50% of the loading dose) will be twice a week subcutaneously weeks 1-8. There will only be two doses per week regardless of being a loading or maintenance dose. In Phase 2- Applicable only for patients in Arm A. I For patients in Phase 2 Arm B (standard RT + TMZ without BMX-001), vital sign evaluation will only be required on days of the History and Physical assessment.

m Arm A: Patients will be monitored at drug administration with vital signs and injection site reaction at pre dose, at 5 (+/-2), 15 (+/-3), 30 (+/-5), and 60 (+/-5) minutes post administration on the BMX-001 loading dose. Patients will be monitored at drug administration with vital signs and injection site reaction at pre dose, at 5 (+/-2), 15 (+/-3) and 30 (+/-5) minutes post administration on BMX-001 maintenance injection days. See Section 0.

o Phase 2 only, subjects will be randomized after all eligibility criteria is confirmed.

p For Phase 2: For subjects in Arm A, this column is the day of the BMX-001 Loading Dose. For Subjects in Arm B, these items should occur -5 to 0 days prior to the start of RT. The procedures for this visit should not take place until final eligibility is confirmed and randomization has occurred.

q In Phase 2, subjects randomized to Arm B will NOT have a Week 7 or Week 8 research study visit.

r In Phase 2, subjects randomized to Arm B do not have a Week 1 study visit, although they will be in the clinic for the start of RT and TMZ.

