## **13.3** Chemoradiation Treatment Period (with and without BMX-001)

The treatment period for BMX-001 is eight weeks. This consists of treatment prior to start of chemotherapy- RT, during the six weeks of concurrent daily TMZ and standard RT with BMX-001 (Phase 1 and Phase 2 (Arm A)) followed by 2 weeks of BMX-001 (Phase 1 and Phase 2 (Arm A)). For subjects in Arm B, this period is six weeks of concurrent daily TMZ with standard RT followed by 2 weeks of no treatment. For subjects in Arm B, they do not need to return to the clinical center for a study visit once TMZ and RT is complete for visits at Week 7 and Week 8.

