#### 13.8.9 Bone Marrow Assessments

Bone marrow function will be assessed by CBC with differential (which includes platelet counts) as described in the table in Section 13 Screening and On-Study Tests and Procedures.

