10.3 POWER FOR THROMBOCYTOPENIA ENDPOINT

10.3.1 ORIGINAL POWER ANALYSIS

Platelet counts will be obtained during radiation and temozolomide treatment and ending 2 weeks after termination of radiation. The percentage of patients within each treatment group that experience grade 3 or 4 thrombocytopenia will be estimated. Gerber [2] reports that 15% of patients who receive standard radiation and temozolomide experience grade 3 or 4 thrombocytopenia. With 80 patients per arm, there is 80% power with a one-tailed chi-square test (α =0.05) to detect a reduction in grade 3 or 4 thrombocytopenia from 15% in Arm B (without BMX-001) to 4% in Arm A (with BMX-001).

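### Both platelet endpoints run to 2 weeks after RT, but Arm B has no week 7 or 8 study visit, so its late platelet counts may be sparser than Arm A's

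*SAP*

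**What the plan says.** **The endpoint window.** SAP 10.1 defines two platelet endpoints, grade 3-4 thrombocytopenia and a count below 100K, both during concurrent TMZ and RT. It adds: "The period of observation for these events will extend until 2 weeks after completion of radiation treatment". Protocol 16.5.2.2 sets the same window. SAP 10.3.1 assumes that the data will exist: "Platelet counts will be obtained during radiation and temozolomide treatment and ending 2 weeks after termination of radiation".

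**The blood counts.** Protocol 13, Table 4, footnote d: "Weekly CBCs and CMPs will begin at week 2 and continue through week 8". Protocol 9.1.7 agrees: "Weekly CBC with differential and CMP will begin at week 2 and continue through week 8". Neither names an arm, and the CBC row of Table 4 is marked in weeks 7 and 8. Protocol 13.8.9 makes that table the source of the marrow data: "Bone marrow function will be assessed by CBC with differential (which includes platelet counts) as described in the table in Section 13".

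**The visits.** Footnote q, attached to the week 7 and week 8 columns of the same table, says: "In Phase 2, subjects randomized to Arm B will NOT have a Week 7 or Week 8 research study visit". Protocol 13.3 says of Arm B that "they do not need to return to the clinical center for a study visit once TMZ and RT is complete". For Arm A, footnote k says that BMX-001 doses "will be twice a week subcutaneously weeks 1-8".

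**Other Arm B contacts.** Protocol 13.8.2 requires an examination, vital signs, weight and KPS two weeks after RT and TMZ, with no arm limit. SAP 4 has cognition measured in all subjects 2 weeks after RT. Protocol 14.1 records Arm B adverse events to 30 days after the last chemotherapy or RT.

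**The concern.** A low platelet count without symptoms is found only if blood is drawn. In the last two weeks of the window Arm A is in clinic twice a week. Arm B is excused from study visits, although its counts appear to be required. No passage says where Arm B's week 7-8 samples are taken or how the results reach the database. If sites followed the visit schedule literally, the two arms would be observed with different intensity over part of the same window.

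The endpoint matters: SAP 4 singles out thrombocytopenia, with cognition, among the secondary endpoints. SAP 10 gives no rule for a treated patient who has no late counts. By contrast, SAP 13.2 states for radiographic response that patients without follow-up stay in the denominator as non-responders. The drop-out analysis in SAP 9.1 covers cognition only. Overall survival is not affected.

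**Working it through.** **1. The schedule, side by side**

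| Item | Arm A | Arm B |
|---|---|---|
| Endpoint window (SAP 10.1) | to 2 weeks after RT | to 2 weeks after RT |
| Weekly CBC (Protocol 9.1.7; Table 4, footnote d) | weeks 2-8 | weeks 2-8, no arm exception stated |
| Week 7-8 study visits (footnotes k and q; 13.3) | yes, with twice-weekly dosing | none |
| Contact about 2 weeks after RT (Protocol 13.8.2; SAP 4) | yes | yes, but 13.8.2 lists no CBC |

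**2. How many counts are exposed**

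Weeks 2 to 8 hold 7 weekly counts. Weeks 7 and 8 are 2 of them: 2/7 = 29%. This is an upper bound. Protocol 9.1.8.1 allows 30-33 fractions at 5 per week, and 33/5 = 6.6 weeks, so a 33-fraction patient in Arm B is still attending for RT in week 7. For that patient the exposed share is nearer 1/7 = 14%. The split between 30 and 33 fractions is not given. These are shares of counts, not of events.

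**3. The plan's own power figure**

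Inputs from SAP 10.3: 15% vs 4% with 80 per arm; revised to 15% vs 3.7% with 71 in Arm B and 78 in Arm A; one-tailed chi-square, alpha 0.05; stated power 80%.

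- Arcsine approximation: 79.9% original, 80.1% revised.
- Exact enumeration: sum the binomial probabilities of all pairs (x in B, y in A) with z > 1.645, where z = (x/71 - y/78) / sqrt[p(1-p)(1/71 + 1/78)] and p = (x+y)/149. Result: 79.3% revised, and 80.1% for the original design with 80 per arm.
- The pooled normal approximation gives 77.1% and 77.3%.

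The stated 80% reproduces under standard methods and is not in dispute.

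**4. Illustration: Arm B events missed (shares assumed)**

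Suppose a share m of Arm B's grade 3-4 events is not captured, none is lost in Arm A, and the patients concerned are scored as non-events. The observed Arm B rate is then 0.15 x (1 - m).

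| m | Arm B observed rate | Exact power |
|---|---|---|
| 0 | 15.0% | 79% |
| 10% | 13.5% | 71% |
| 20% | 12.0% | 61% |
| 30% | 10.5% | 49% |

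The documents give no value for m. The only event timing they report is two grade 1 cases in week 6 of Phase 1 (Protocol 7.4). Those patients were on BMX-001, so the cases give no missed share for controls.

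**5. Tipping point at the expected counts**

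Expected events: Arm B 71 x 0.15 = 10.65, about 11; Arm A 78 x 0.037 = 2.9, about 3. SAP 10.2 allows chi-square or Fisher's exact test.

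| Arm B vs Arm A events | Chi-square, one-tailed p | Fisher, one-tailed p |
|---|---|---|
| 11 vs 3 | 0.0075 | 0.015 |
| 10 vs 3 | 0.013 | 0.026 |
| 9 vs 3 | 0.024 | 0.046 |
| 8 vs 3 | 0.042 | 0.078 |
| 7 vs 3 | 0.071 | not needed |

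For 8 vs 3: p = 11/149 = 0.0738; z = (0.1127 - 0.0385)/0.0429 = 1.73. Significance is lost with 4 missed Arm B patients by chi-square (4/11 = 36%) and with 3 by Fisher (3/11 = 27%). One or two missed patients would not change the result.

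**6. What a truncated analysis would cost**

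If 10, 20 or 30% of events in both arms fall after RT (again assumed), removing them from both arms lowers exact power from 79% to 75, 70 or 65%.

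**The case against.** The strongest reply is that nothing here forbids a count. Footnote q and Section 13.3 remove a study visit, not a blood test. The CBC row stays marked in weeks 7 and 8, and two passages require counts through week 8. Arm B samples could be drawn as standard of care and entered in full. That stands, and it is why this is a risk and not a defect in the data. What remains is that capture is unspecified. Footnote q on the week 7-8 columns could equally be read as making the CBC row Arm A only.

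A reader might infer that only Arm A is seen late in the window. The documents do not support that: Protocol 13.8.2 and SAP 4 give Arm B a contact about 2 weeks after RT. But 13.8.2 lists no CBC, and one contact does not replace weekly counts.

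Safeguards exist. Adverse event recording to 30 days partly covers grade 3-4 events. It covers the below-100K endpoint less well, because Protocol 14.1 leaves laboratory findings without clinical significance unrecorded. Protocol 16.5.4 names data completeness among the purposes of its additional interim analyses. Its June 2020 platelet look at the first 80 patients includes a check of counts against adverse event reports. Neither is specified by arm and week, which is what would settle the question.

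It is also fair to say that the 10-30% shares have no anchor in the documents. They show sensitivity and do not estimate a loss.

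**Conclusion.** The point holds as a low-cost improvement. The window and the count schedule are the same in both arms, but the visit schedule is not, and the passages are not reconciled. Arm B's late platelet ascertainment may therefore be sparser. The exposure is at most 2 of 7 scheduled counts, nearer 1 of 7 for 33-fraction patients. If capture was complete, nothing is lost.

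Two stronger readings should be resisted. A reader might infer that 29% of Arm B events are missing; that figure is a ceiling on scheduled counts and says nothing about events. A reader might also infer that any bias must run against BMX-001 and so could never create a false protection claim. That is true only if Arm B patients without late counts are scored as non-events. If they are excluded, the direction is undetermined, and SAP 10 does not say which applies.

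The power and tipping-point figures rest on assumed missed shares, no loss in Arm A, and scoring as non-events. They show that 3 or 4 uncaptured Arm B cases could change the conclusion at the expected counts, not that this happened.

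**What to change.** 1. Reconcile Protocol 9.1.7 and Table 4 footnote d with footnote q, 13.3 and 13.8.2 on Arm B's week 7-8 counts, and state how those results reach the database.
2. Before database lock, enter any existing local laboratory platelet counts for those weeks.
3. Keep the prespecified window as the main analysis, and state how patients without late counts are handled.
4. Report the number of platelet counts obtained by arm and week.
5. Add one supportive analysis of both platelet endpoints, truncated at each patient's own last RT date, the period scheduled alike in both arms. A fixed week 6 cut would not do, because 33 fractions end in week 7.

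The cost is some SAP wording, one table, one supportive analysis and retrieval of existing results; no new draws or visits are proposed. The truncated analysis has fewer events (power about 75, 70 or 65% under the assumed 10, 20 or 30%) and omits the last 2 weeks of BMX-001 dosing, so it should be supportive only.

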10.2 METHOD OF ANALYSIS

For both endpoints described in Section 10.1, a chi-square or Fisher's exact test will be conducted to compare the prevalence of such thrombocytopenia observed in patients with and without BMX-001.

10.3 POWER FOR THROMBOCYTOPENIA ENDPOINT

10.3.1 ORIGINAL POWER ANALYSIS

Platelet counts will be obtained during radiation and temozolomide treatment and ending 2 weeks after termination of radiation. The percentage of patients within each treatment group that experience grade 3 or 4 thrombocytopenia will be estimated. Gerber [2] reports that 15% of patients who receive standard radiation and temozolomide experience grade 3 or 4 thrombocytopenia. With 80 patients per arm, there is 80% power with a one-tailed chi-square test (α =0.05) to detect a reduction in grade 3 or 4 thrombocytopenia from 15% in Arm B (without BMX-001) to 4% in Arm A (with BMX-001).

10.3.2 REVISED POWER ANALYSIS

For this endpoint to have relevance, a patients must have received some treatment with temozolomide and radiation in either Arm A or B. At this point, analyses suggest that 78 patients in Arm A and 71 patients in Arm B received protocol treatment. With 78 and 71 patients in Arms A and B, respectively, there is 80% power with a one-tailed chi-square test (α =0.05) to detect a reduction in grade 3 or 4 thrombocytopenia from 15% in Arm B (without BMX-001) to 3.7% in Arm A (with BMX-001).

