# 11.4 Administration

TMZ is administered orally on an empty stomach. The drug is approximately 100% bioavailable. The dose will be rounded to the nearest 5 mg when possible. Final dose will be determined by the subject's primary neuro-oncologist and the following can be taken into account: number of pills per day and number of co-payments required. Effects of food on product absorption are not yet known. **DO NOT OPEN CAPSULES. DO NOT MIX WITH FOOD. DO NOT CHEW CAPSULES.** 

TMZ at a dose of 75mg/m^2 po daily will be started with external beam RT (+/- 5 days). TMZ will be held according to standard of care for the institution (typically when platelets drop below 100,000 cells/uL), grade 4 neutropenia, or grade 4 non-hematologic toxicity secondary to TMZ. TMZ will be restarted at 50 mg/m^2 after resolution of the toxicity, or  $\leq$  grade 1. If the grade 3 thrombocytopenia, grade 4 neutropenia, or grade 4 non-hematologic toxicity secondary to TMZ recurs at 50 mg/m^2, TMZ will be held during RT therapy, but may resume after RT therapy if the patient meets the treatment criteria.

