6 ANALYSIS POPULATIONS

The following populations will be identified:

• Intent to Treat Population (ITT): All patients randomized into the clinical trial, regardless of compliance.

¹ During study accrual, a new WHO classification system for CNS tumors was published [1]. Though the classification system in use at the time of study activation was used throughout the conduct of the study, the classification of all patients under the new WHO 2021 system will also be described.

- Safety Population: All patients who received at least one dose of BMX-001 or temozolomide
- Treated Population: All patients who completed chemoradiation with or without BMX-001. BMX-001 must be given for at least 6 weeks (or 13 doses).
- PK Population: Subjects who participated in the PK portion of the study (n=6).

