19 DESCRIPTION OF TABLES FOR REPORTING

The following tables and figures will be produced, source data listings will be provided

Description	Population		
Summary of Subject Disposition	ITT, Safety, Treated		
Summary of Important Protocol Deviations*	Safety		
DEMOGRAPHICS			
Summary of Demographic Characteristics	ITT, Treated		
SAFETY DATA	1		
Summary of All AEs	Safety		
Summary of TEAEs	Safety		
Summary of BMX-001 Related TEAEs	Safety		
Summary of Baseline AEs	Safety		
Summary of all AEs	Safety		
Summary of SAEs/Deaths	Safety		
Narratives of SAEs	Safety		
Summary of Pre and Post dosing Vital Signs	Safety		
Listing of Abnormal ECG findings post BMX-001 treatment	Safety		
Summary of clinically significant:	Safety		
 Clinical Laboratory Evaluations Physical Examinations: Abnormal physical examination findings 	Safety		
PK*	PK		
OUTCOMES			
os	ITT, Treated		
PFS	ITT, Treated		
Thrombocytopenia	ITT, Treated		
Cognitive Testing	ITT, Treated		
HRQoLs	ITT, Treated		
OTHER			
Treatment Disposition: TMZ, RT, BMX-001	Safety		

Treatment Exposure: TMZ, RT, BMX-001	Safety
Concomitant Medications	Treated
Analysis Sets, including subjects excluded from analysis	All
List of Withdrawals	All

^{*=} BioMimetix will provide

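### SAP 10.3.2 ties the thrombocytopenia endpoint and its power to patients who received temozolomide and radiation, but SAP 19 reports it in ITT and Treated, and neither is that group

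*SAP*

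**What the plan says.** SAP 4 names thrombocytopenia as one of two secondary endpoints of particular interest. SAP 10.1 defines two proportions per arm, grade 3 or 4 thrombocytopenia and a platelet count below 100K, each observed until 2 weeks after radiation ends. SAP 10.2 compares them by chi-square or Fisher's exact test. Neither section names an analysis population, and nor does Protocol 16.5.2.2.

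SAP 10.3.2 sets an exposure condition: "a patients must have received some treatment with temozolomide and radiation in either Arm A or B". It reports that "78 patients in Arm A and 71 patients in Arm B received protocol treatment" and states that with these numbers "there is 80% power with a one-tailed chi-square test" at α = 0.05 to detect a fall from 15% (Arm B) to 3.7% (Arm A).

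The list in SAP 19 reads "Thrombocytopenia ITT, Treated". By SAP 6, ITT is everyone randomised. Treated is "All patients who completed chemoradiation with or without BMX-001", with a further minimum of 6 weeks or 13 doses of BMX-001. The Safety Population, at least one dose of BMX-001 or temozolomide, is not listed for this endpoint.

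Under Protocol 11.4, temozolomide is held for toxicity, typically when platelets fall below 100,000, and restarted at a lower dose on resolution. If the toxicity recurs, "TMZ will be held during RT therapy, but may resume after RT therapy if the patient meets the treatment criteria".

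**The concern.** Exposure to temozolomide is a precondition of an endpoint about temozolomide-induced marrow toxicity, as SAP 10.3.2 itself says. The reporting list nevertheless uses one set that is wider than the exposed group and one that is narrower.

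- **ITT** includes randomised patients who never started temozolomide. They cannot have the event the endpoint is about, and a proportion over all randomised patients leaves them in the denominator.
- **Treated** is defined by completing treatment, which is known only after randomisation. Low platelets are a reason to interrupt or stop temozolomide, so a patient can leave this set because the endpoint occurred. For the second endpoint, the platelet threshold is the typical hold threshold itself.

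At stake is an endpoint of declared interest in an open-label trial. It would be reported in two tables that may disagree, with no rule on which is the main one. Neither is the analysis to which the power statement applies.

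**Working it through.** **Inputs.** Exposed patients: 78 (A) and 71 (B), SAP 10.3.2. Rates: 3.7% (A) and 15% (B), SAP 10.3.2. One-tailed chi-square, α = 0.05. Randomised: 160 in total (SAP 8.4.2), with a goal of 80 per arm (SAP 4). The actual count per arm is not stated.

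**1. Reproduce the stated power.** With x events of 71 in B, y of 78 in A and p̄ = (x + y)/149, reject when

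z = (x/71 − y/78) / √[p̄(1 − p̄)(1/71 + 1/78)] > 1.645.

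Summing the binomial probabilities of all (x, y) that reject gives 79.3%, in line with the stated 80%. The same method gives 80.1% for the original 80 v 80 at 15% v 4%. The normal approximation gives 77.3% for 71 v 78. If the Fisher option in SAP 10.2 were used, one-sided power would be about 71%; that is a separate matter.

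**2. ITT, assuming 80 per arm and never-dosed patients counted as event-free.**

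- Never dosed: 80 − 78 = 2 (A); 80 − 71 = 9 (B).
- Expected events: 0.037 × 78 = 2.886 (A); 0.15 × 71 = 10.65 (B).
- ITT rates: 2.886/80 = 3.6% (A); 10.65/80 = 13.3% (B).
- Difference: 9.7 points, against 15 − 3.7 = 11.3 in the exposed group.
- Exact power: 74.9% (normal approximation 71.5%).

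With no drug effect and 15% in both exposed groups, ITT would show 0.15 × 78/80 = 14.6% (A) v 0.15 × 71/80 = 13.3% (B). That is 1.3 points against BMX-001, and the one-sided rejection rate falls from 5.0% to 2.9%.

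**3. Sensitivity to the per-arm count.** With a randomised to Arm A out of 160, never-dosed numbers are a − 78 (A) and 89 − a (B). Arm B has more unless a ≥ 84. From 78/82 to 82/78 (A/B), the never-dosed split runs from 0 v 11 to 4 v 7. ITT power by the normal approximation runs from 68% to 75%, against 77.3% in the exposed group by the same formula.

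**4. Treated.** No document figure says how many event patients fail to complete. Two illustrations with invented loss fractions, removing event patients only, show that even the direction is open:

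- Half the event patients lost in each arm: B = 5.325/65.675 = 8.1%; A = 1.443/76.557 = 1.9%. The gap is 6.2 points, narrower than 11.3.
- Half lost in A, one tenth in B: A = 1.443/76.557 = 1.9%; B = 9.585/69.935 = 13.7%. The gap is 11.8 points, wider than 11.3.

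**The case against.** A reader might infer that both listed sets lower the Arm B rate and shrink the apparent protection, with a large loss of power in Treated. The documents do not support that for Treated:

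- SAP 6 does not define completed chemoradiation, and its only numeric minimum is for BMX-001. A patient whose temozolomide was held and restarted may count as a completer.
- Only recurrence of the toxicity keeps temozolomide off for the rest of radiation. The endpoint window runs 2 weeks past radiation, so some events come too late to prevent completion.
- BMX-001 is itself held for grade 3 thrombocytopenia (Protocol 13.4.1), and the dose minimum applies in Arm A only. Arm A could therefore lose proportionally more event patients, which can widen the gap. Removing non-completers without an event also raises a rate.

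On ITT, the effect is modest and works against the drug's claim. Section 10 does not say that never-dosed patients count as event-free; the explicit rule of that kind (SAP 13.2) is for radiographic response. They could be treated as not evaluable, but the table would then be the SAP 10.3.2 group and not ITT as defined. The 2 v 9 split rests on 80 per arm, and at 82/78 it is 4 v 7.

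SAP 11.2.1 already tabulates treatment-emergent adverse events in the Safety Population over a window ending at the same point. That helps, but it is not the between-arm test of either platelet endpoint.

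These limits remove any claim about the size or direction of the Treated bias. They leave the mismatch between SAP 10.3.2 and SAP 19 in place.

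**Conclusion.** The concern holds as a mismatch between the group in which SAP 10.3.2 says the endpoint is relevant and powered, and the two sets in which SAP 19 reports it.

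For ITT the cost is about 1.6 points of difference (11.3 to 9.7) and about 4 points of exact power (79.3% to 74.9%). This is conditional on the SAP's rates, 80 randomised per arm, and never-dosed patients counted as event-free.

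For Treated the defect is one of principle: membership can depend on the outcome being measured. The documents do not allow its size or direction to be determined, and the loss fractions used above are illustrations only.

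The change should be made, because following the plan as written gives no table that matches its own relevance condition.

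**What to change.** In SAP 10.2, state that the main analysis of both platelet endpoints includes all randomised patients who received some temozolomide and radiation, analysed by assigned arm, which is the SAP 10.3.2 group. In SAP 19, list that set first for thrombocytopenia and label ITT and Treated as supportive or sensitivity analyses only. State how never-dosed patients are counted in the ITT version.

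The Safety Population is close but not identical, since it could include an Arm A patient given only BMX-001.

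The cost is one or two sentences and one table cell, with no new data. The small downside is that the main set depends on starting treatment, which SAP 10.3.2 already accepts.
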